## 10.2 Objective 2 Paper

**Figure 1.** Cohort identification of patients for the primary and larger secondary sample of the PROUD Trial effectiveness analyses

**Supplemental Figure 1.** Samples of patients in the primary and secondary Objective 2 analysis

HCS = health care system

rand. = randomization

\* OUD diagnosis anywhere in the health system

\*\* Defined by having any visit, diagnosis, or procedure

**Table 1.** Characteristics of primary care patients with documented OUD who visited PROUD trial clinics (Effectiveness Objective Samples)

Characteristic	Pre-randomization Sample: Patients in Trial Clinics with Documented OUD Pre-randomization		Post-randomization Sample a, b : Patients New to Trial Clinics or with Newly Documented OUD Post-randomization	
	Intervention	Usual Care	Intervention	Usual Care
	(N = )	(N = )	(N = )	(N = )
	%			
Age at randomization, years				
16-17				
18-24				
25-44				
45-64				
65-74				
75+				
Female				
Race/ethnicity				
Hispanic ethnicity				
Non-Hispanic				
Asian				
Black or African American				
American Indian / Alaska Native				
Native Hawaiian or Pacific				
Islander				
White				
Multiple race				
Other race				
Missing race and ethnicity data				

**Table 1.** Characteristics of primary care patients with documented OUD who visited PROUD trial clinics (Effectiveness Objective Samples)

Characteristic	Pre-randomization Sample: Patients in Trial Clinics with Documented OUD Pre-randomization		Post-randomization Sample a, b : Patients New to Trial Clinics or with Newly Documented OUD Post-randomization	
	Intervention (N = )	Usual Care (N = )	Intervention (N = )	Usual Care (N = )
Insurance status closest to randomization b				
Medicare				
Medicaid				
Otherwise insured (e.g., commercial, private)				
Uninsured				
Unknown				
Unstable housing including homelessness b				
Socioeconomic status variables using zip code closest to randomization, median (IQR)				
Median household income				
% unemployed				
% below federal poverty level				
Comorbidity in the two years pre-randomization b				
Alcohol use disorder				
Other (non-opioid) substance use disorder				
Schizophrenia and other psychotic disorders				

**Table 1.** Characteristics of primary care patients with documented OUD who visited PROUD trial clinics (Effectiveness Objective Samples)

Characteristic	Pre-randomization Sample: Patients in Trial Clinics with Documented OUD Pre-randomization		Post-randomization Sample a, b : Patients New to Trial Clinics or with Newly Documented OUD Post-randomization	
	Intervention	Usual Care	Intervention	Usual Care
	(N = )	(N = )	(N = )	(N = )
Baseline OUD treatmentb				
Days of treatment per year, mean (IQR)				
OUD treatment duration				
0 days				
1-30 days				
31-90 days				
91-180 days				
180+ days (sustained OUD treatment)				
Baseline acute care utilizationb				
Days of acute care utilization per year, mean (IQR)				
Days hospitalized c				
Days of emergency care d				

**Table 1.** Characteristics of primary care patients with documented OUD who visited PROUD trial clinics (Effectiveness Objective Samples)

Characteristic	Pre-randomization Sample: Patients in Trial Clinics with Documented OUD Pre-randomization		Post-randomization Sample a, b : Patients New to Trial Clinics or with Newly Documented OUD Post-randomization	
	Intervention (N = )	Usual Care (N = )	Intervention (N = )	Usual Care (N = )
Proportion of patients with:				
Any acute care				
Hospitalization c				
Never				
Once				
2-3 times				
4+ times				
Emergency care visit d				
Never				
Once				
2-3 times				
4+ times				

HCS = health care system

a Includes patients in the trial clinics without an OUD diagnosis pre-randomization who had an OUD diagnosis post-randomization, patients in the HCS (but not in the trial clinics) with an OUD diagnosis pre-randomization or post-randomization, and patients who were new to the HCS post-randomization (see Supplemental Figure)

b Patients in the HCS pre-randomization use baseline values of time-varying covariates; patients new to HCS post-randomization do not have baseline values of time-varying covariates (insurance status and zip code use post-baseline measure available closest to randomization date; clinical characteristics use two years post-randomization; baseline treatment and outcomes not available)

c Days hospitalized also includes emergency department or urgent care visits that resulted in a hospitalization. [Report % of hospitalizations that started in (or immediately preceded) an emergency visit.]

d Emergency care includes visits to an emergency department or urgent care facility that did not result in hospitalization

**Table 2.** Effect of PROUD Intervention on OUD treatment among patients with documented OUD pre-randomization

Measure of OUD treatment in 2 years post-randomization	Intervention (n=xxx)	Usual Care (n=xxx)	Treatment effect a		P value
Main treatment measure: days of OUD treatment c	mean (IQR) days per year b		RR	95% CI	
Primary sample with OUD pre-randomization (intention to treat)					
Sub-samples and/or follow-up periods restricted to:					
a. Clinics that successfully implemented MA model d					
b. Time period in which the NCM was seeing patients					
c. Patients with PC visit to assigned clinic post-randomization					
d. Both b and c					
Secondary treatment measures	N (%) b		OR	95% CI	
OUD treatment duration					
0 days					
1-30 days					
31-90 days					
91-180 days					
180+ days (sustained OUD treatment)					
Initiation of new episode of OUD treatment e					
Initiated and 80% adherence to treatment					
Initiated and sustained OUD treatment					

a Estimated from a mixed-effect model with clinic-specific random intercept, adjusted for days of OUD treatment during the baseline period

b Unadjusted estimates. We note that if we observe a statistically significant difference from the adjusted model, but the unadjusted estimates appear similar then we plan to also calculate the adjusted estimates

c OUD treatment defined as having a medication order or procedure code for buprenorphine formulations that are indicated for OUD or having a medication order or procedure code for XR-NTX and 2+ visits with diagnosis code for OUD or opioid overdose during the pre-randomization period.

d Successful implementation is defined as the NCM at the intervention clinic at that HCS seeing at least 30 patients. We note that estimates from the secondary analyses of the main treatment measure may instead be separated into a different paper or included in a supplemental table.

e OUD treatment following a period of 365 days with no OUD treatment

**Table 3.** Effect of PROUD Intervention on acute care utilization among primary care patients with documented OUD pre-randomization

Measure of Acute Care Utilization in 2 years post-randomization	Intervention	Usual Care	Treatment	95% CI	P value
	(n=xxx)	(n=xxx)	Effect a		
	mean (IQR) days per year b		RR		
Primary outcome: days of acute care utilization (intention to treat)					
Sub-samples and/or follow-up periods restricted to:					
a. Clinics that successfully implemented MA model c					
b. Time period in which the NCM was seeing patients					
c. Patients with PC visit to assigned clinic post-randomization					
d. Both b and c					
Days of hospitalization d (intention to treat)					
Sub-samples and/or follow-up periods restricted to:					
a. Clinics that successfully implemented MA model c					
b. Time period in which the NCM was seeing patients					
c. Patients with PC visit to assigned clinic post-randomization					
d. Both b and c					
Days of emergency care e (intention to treat)					
Sub-samples and/or follow-up periods restricted to:					
a. Clinics that successfully implemented MA model c					
b. Time period in which the NCM was seeing patients					
c. Patients with PC visit to assigned clinic post-randomization					
d. Both b and c					

**Table 3.** Effect of PROUD Intervention on acute care utilization among primary care patients with documented OUD pre-randomization

Measure of Acute Care Utilization in 2 years post-randomization	Intervention (n=xxx)	Usual Care (n=xxx)	Treatment Effect a	95% CI	P value
	mean (IQR) days per year b		RR		
Proportion of patients with:	N (%) b		OR		
Any acute care					
Hospitalization d					
Never					
Once					
2-3 times					
4+ times					
Emergency care visit e					
Never					
Once					
2-3 times					
4+ times					

a Estimated from a mixed-effect model with clinic-specific random intercept, adjusted for the baseline value of the outcome (binary/categorical measures adjust for the continuous value of the measure)

b Unadjusted estimates. [We note that if we observe a statistically significant difference from the adjusted model, but the unadjusted estimates appear similar then we plan to also calculate the adjusted estimates.]

c Successful implementation is defined as the NCM at the intervention clinic at that HCS seeing at least 30 patients. [We note that estimates from the secondary analyses of the main treatment measure may instead be separated into a different paper or included in a supplemental table.]

d Days hospitalized also includes emergency department or urgent care visits that resulted in a hospitalization. [Report % of hospitalizations that started in (or immediately preceded) an emergency visit.] Specific cut-points for categorization to be determined based on empirical distribution at baseline

e Emergency care includes visits to an emergency department or urgent care facility that did not result in hospitalization; specific cut points for categorization to be determined based on empirical distribution at baseline

**Table 4.** Observational analysis of effect of PROUD Intervention on OUD treatment in the larger secondary sample that includes patients with newly recognized OUD in trial clinics post-randomization

Measure	Pre-randomization Sample: Patients in Trial Clinics with Documented OUD Pre- randomization a		Post-randomization Sample: Patients New to Trial Clinics or with Newly Documented OUD Post-randomization				Secondary Sample (Overall)
	Treatment effect b	95% CI	Intervention	Usual Care	Treatment effect b	95% CI	Omnibus P value c

Same measures as Table 2

a Estimating the same thing as Table 2, but adjusted for demographics and not adjusting for baseline (which is not measured among patients new to the health system post-randomization); likely will be omitted from main paper (include in supplement instead)

b Estimated from a mixed-effect model with clinic-specific random intercept and an interaction term between the intervention effect and the timing of when the patient was first seen in the trial clinic with diagnosed OUD (pre- or post-randomization) and adjusted for demographics

c Testing for whether there is a difference between intervention and usual care clinics for either subset of patients (primary sample or secondary sub-sample added to the primary sample)

**Table 5.** Observational analysis of intervention effect on acute care utilization in the larger secondary sample including patients with newly recognized OUD in trial clinics post-randomization

Measure	Pre-randomization Sample: Patients in Trial Clinics with Documented OUD Pre- randomization a		Post-randomization Sample: Patients New to Trial Clinics or with Newly Documented OUD Post-randomization		Secondary Sample (Overall)		
	RR b	95% CI	Intervention	Usual Care	Treatment Effect b	95% CI	Omnibus P value c
Same measures as Table 3							

a Estimating the same thing as Table 3, but adjusted for demographics and not adjusting for baseline (which is not measured among patients new to the health system post-randomization); likely will be omitted from main paper

b Estimated from a mixed-effect model with clinic-specific random intercept and an interaction term between the intervention effect and the timing of when the patient was first seen in the trial clinic with diagnosed OUD (pre- or post-randomization) and adjusted for demographics

c Testing for whether there is a difference between intervention and usual care clinics for either subset of patients (primary sample or secondary sub-sample added to the primary sample)

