### 5.3 Primary Analytic Method for Objective 2 Primary Effectiveness Outcome Measure

Our primary outcome for the main Objective 2 (effectiveness) outcome is a patient-level measure of the number of days of acute care utilization over the follow-up period, which is a 2-year period for 5 of the 6 HCSs, and a 1.5-year period for the 6th HCS.

The primary analysis will be among individuals with an eligible PC visit pre-randomization who had an OUD diagnosis during the pre-randomization period (see definition of “Objective 2 primary study sample” in Section 3). The patient-level analysis will follow ITT principles, with patients analyzed according to the randomization group of the clinic to which they were assigned pre-randomization, regardless of the degree to which the clinic actually implemented the intervention, and regardless of whether the patient was actually treated by the NCM or seen post randomization.

We hypothesize that, among patients who had an eligible PC visit and were identified as having an OUD diagnosis pre-randomization (documented in their EHRs up to 3 years prior to randomization), individuals from a PROUD intervention clinic will have decreased acute care utilization after randomization as compared to individuals from a UPC clinic. We plan to fit a mixed-effect Poisson regression model (with log link) at the patient level to the number of days of acute care utilization. The model will account for clustering of patients within a clinic by including clinic-specific random intercepts. Specifically, the regression model will be of the following form:

$$\log[E(y_{ijk})] = \log(\text{days}_j) + \alpha + \beta * trt_{ij} + \gamma * z_{ijk} + \theta_{ij}$$

where

- $y_{ijk}$  is the observed number of days of acute care utilization of patient  $k$  in clinic  $i$  of HCS  $j$  over the follow-up period
- $trt_{ij}$  is the treatment indicator (PROUD intervention) for clinic  $i$  in HCS  $j$
- $z_{ijk}$  is the baseline value of the outcome during the two years prior to randomization for patient  $k$  in clinic  $i$  of HCS  $j$  ( $\gamma$  is the corresponding coefficient)
- $\theta_{ij}$  is the random effect for clinic  $i$  in HCS  $j$

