#### **5.5.1 Rationale for Conducting Analyses Within a Secondary Sample**

It is expected that some of the patients who initiate treatment in PROUD intervention clinics will have been diagnosed with OUDs after randomization, potentially due to the PROUD intervention. It is also possible that patients may be newly attracted to the clinic (or to the health system entirely) potentially because of the PROUD intervention (based on the fact that at least 77% of patients treated in MA were new to the clinic after implementation). The primary analysis of Objective 2 described above would miss any impact of the PROUD intervention on both of these subsamples of patients, because they were not identified pre-randomization (because they were not previously diagnosed with OUDs or because they did not visit the clinic in the pre-randomization period). These secondary analyses within the secondary Objective 2 study sample, which includes patients seen in the trial clinics with an OUD diagnosis post-randomization only, are designed to capture these additional patients who may be affected by the PROUD intervention.

On the other hand, these secondary analyses must account for the fact that patients with newly recognized OUD in the PROUD intervention clinics post-randomization are likely to differ markedly from patients with newly recognized OUD in the UPC clinics post-randomization. Further, it is likely that these patients could differ in ways that may be associated with acute care utilization (e.g., patients could be referred for ongoing buprenorphine treatment from an ED or hospital that started treatment). To address this, analyses will adjust for covariates known or hypothesized to be associated with acute care utilization (based on prior literature), as well as secondarily for any additional covariate observed to differ across patients with newly recognized OUD post-randomization in the UPC versus PROUD intervention clinics.

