### **5.5.2 Defining Covariates for the Objective 2 Secondary Sample That Includes Patients Not Seen in the Health System Pre-randomization**

Defining covariates using pre-randomization data is preferred for randomized studies, because this ensures that the intervention does not affect the covariate values. However, this is not possible for patients who were not seen in the HCS pre-randomization. For these patients we therefore plan to use the post-randomization value of time-varying covariates that is available closest to randomization. We note that using this approach means that analyses including patients new to the HCS post-randomization cannot adjust for “baseline” acute care utilization (since patients new to the HCS post-randomization do not have baseline data observed). We considered applying a multiple imputation approach to address missing baseline data among these patients; however, we did not think the missing at random (MAR) assumption was reasonable (i.e., we did not think using data from patients in the HCS pre-randomization was sufficient to impute data from patients new to the HCS). Therefore, sensitivity analyses will be applied to examine the subpopulation excluding these patients (see Section 5.5.4).

Decisions regarding the set of covariates to be included in analyses within this secondary sample (listed below) were made in conjunction with the Investigator team to determine whether individual covariates measured post-randomization are likely to be impacted by the intervention. We wanted to avoid including covariates that are likely to be impacted by the intervention (as they may be on the causal pathway). Although documentation of certain comorbidities were thought to be most likely to be impacted by the intervention, it was hypothesized that documentation of any comorbidities could be increased via the intervention due to increased care in general; insurance status was also plausibly thought to be related to intervention status (as poor OUD-related outcomes could affect insurance status).

Covariate adjustment: We plan to adjust for the following subset of covariates as in the secondary analysis within the primary Objective 2 sample (described above in Section 5.4.1):

- 1) age (at randomization, including linear and quadratic terms)
- 2) gender (F/M)
- 3) race/ethnicity (Hispanic, Asian, Black or African American, White, Other, Unknown)

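### The full-sample Objective 2 secondary model omits the baseline value of the outcome for every patient, although only patients new to the health system lack it

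*SAP*

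**What the plan says.** The primary Objective 2 model (SAP 5.3) carries a patient-level covariate that "is the baseline value of the outcome during the two years prior to randomization for patient" k. It is fitted in patients with a primary care visit and an OUD diagnosis before randomization, and reported in Table 3.

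The secondary sample adds patients whose OUD was first recognized in the trial clinics after randomization. SAP 5.5.2 states that "using this approach means that analyses including patients new to the HCS post-randomization cannot adjust for" baseline acute care, because "patients new to the HCS post-randomization do not have baseline data observed". Multiple imputation was considered and rejected because missing at random was judged unreasonable. The covariates retained are age, gender, race/ethnicity and neighborhood SES. SAP 5.5.3 puts that one set into the model for all patients, with a period indicator, its interaction with arm, and a likelihood ratio test of β0 = β1 = 0. Note a to Table 4 says the pre-randomization column is "adjusted for demographics and not adjusting for baseline (which is not measured among patients new to the health system post-randomization"); note a to Table 5 describes its own as "Estimating the same thing as Table 3, but adjusted for demographics and not adjusting for baseline" and adds that the column "likely will be omitted from main paper".

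SAP 5.5.4.a repeats the analysis in secondary-sample patients who were in the HCS before randomization, with the full 5.4.1 covariates (which build on baseline acute care days), and again with the reduced set.

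**The concern.** It does not follow from some patients having no baseline that an analysis containing them cannot use the baseline of the others. The full-sample model drops a value that has been collected, for patients who have it.

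Two different things are at stake. In the pre-randomization sample the arms are randomized, so omitting baseline costs precision and leaves chance imbalance uncorrected; it does not introduce confounding. In the post-randomization sample the arms are not comparable by design. SAP 5.5.1 says the analysis must account for that and gives as an example that "patients could be referred for ongoing buprenorphine treatment from an ED or hospital that started treatment". Prior acute care is a measured variable close to that route, and the full-sample model leaves it out. The additional covariates listed for the sensitivity analysis in 5.5.2 (insurance, comorbidity, housing) do not name it either.

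The protocol had intended otherwise. Protocol 11.2.2.2 carries the primary Objective 2 covariates into this model, and Protocol 11.2.2.1 lists prior utilization among them.

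**Working it through.** **1. Who has a baseline value.** Note b to Table 1 in SAP 10.2 says patients in the HCS before randomization use baseline values, and that baseline treatment and outcomes are unavailable only for patients new to the HCS. SAP 8.1 treats an unrecorded event as not having occurred, so an in-HCS patient with no recorded acute care has a baseline of zero, not a missing one.

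**2. What each planned analysis covers.**

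| Analysis | Pre-randomization patients | Newly recognized, in HCS | New to HCS | Baseline of outcome |
|---|---|---|---|---|
| 5.3 (Table 3) | yes | no | no | yes |
| 5.5.3 (Tables 4, 5; omnibus test) | yes | yes | yes | no |
| 5.5.4.a, full covariates | yes | yes | no | yes |
| 5.5.4.a, reduced covariates | yes | yes | no | no |

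No planned analysis keeps all three groups and uses the baseline of the two that have it. There is also no table shell for 5.5.4.a and no rule for which estimate leads if it disagrees with Table 5.

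**3. Whether the term can be fitted.** Let h = 1 if the patient was in the HCS before randomization and 0 otherwise, and b the baseline value. Add γ_b·b·h + δ·(1 − h) to the linear predictor. For new patients b is multiplied by zero and δ gives them their own level, so nothing is imputed and the missing-at-random objection does not arise. The smaller alternative, b × (1 − period), is zero for every post-randomization patient. It restores adjustment for β0 and its part of the omnibus test and does nothing for confounding.

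**4. Precision, by assumption.** The nearest stated figure is SAP 6.2.2: more than 80% power at RR 0.65 with clinic SD τ = 0.23. Re-simulating (12 stated clinic sizes, total 1,245; mean 4.0 × 2.04 = 8.16 days; Poisson mixed model; two-sided Wald test on t with 10 df; 1,000 repetitions) gives 86%, consistent with the SAP. Type I error was 0.083 against the stated 0.070.

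That power model has no baseline term, so τ = 0.23 represents unadjusted clinic variation. With 6 clinics per arm, the clinic part of SE(log RR) = 0.23 × √(2/6) = 0.133. The documents do not say how much clinic variance baseline explains. Under assumed shares:
- 25%: 0.133 × √0.75 = 0.115
- 50%: 0.133 × √0.50 = 0.094
- 75%: 0.133 × √0.25 = 0.066

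By simulation the empirical SE falls from about 0.14 to 0.10 at a 50% share (τ = 0.163), and power at RR 0.80 rises from 36% to 57%. These runs use pre-randomization clinic sizes only, so they indicate direction and rough scale for β0, not the performance of the pooled model.

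**5. Confounding, by assumption.** Suppose newly recognized in-HCS patients in intervention clinics had 1.5 times the prior acute care of those in usual care, and follow-up use varies as prior use to a power between 0.3 and 0.7. With no intervention effect the unadjusted rate ratio in that group would be 1.5^0.3 = 1.13 to 1.5^0.7 = 1.33. Table 5 mixes this group with patients new to the HCS in unknown proportion, so this is not the bias in the reported estimate.

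**The case against.** The best reply is that SAP 5.5.4.a already addresses the limitation. It adjusts in-HCS patients for baseline, and its second run separates the effect of changing the sample from that of changing the covariates. This stands, and it rules out reading the plan as never adjusting these patients. But 5.5.4.a excludes patients attracted from outside the system, one of the groups the secondary sample exists to capture, and leaves the full-sample test as it was.

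A reader might infer that Table 5 contradicts Table 3. It does not: the two use different, disclosed covariate sets and may differ numerically. The Table 5 pre-randomization column is expected to be left out of the main paper, and the primary effect remains the baseline-adjusted one.

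A reader might also take 5.5.1 as naming prior acute care as the confounder. It offers hospital or ED referral as an example, and a referral during follow-up may fall outside the two-year baseline window, so baseline would capture that route only in part.

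Finally, SAP 5.5.2 avoids covariates the intervention could affect, and I(new to HCS) might look like one. Whether a patient was in the HCS before randomization is fixed at randomization; what the intervention may change is who enters the sample, which is equally true of the period term already in the model. The indicator method in SAP 8.1 shows a related device is acceptable to the team, but it is stated for categorical covariates and does not settle the matter.

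**Conclusion.** The point holds for the main full-sample model only. SAP 5.5.2 overstates what is impossible: baseline can be used for every patient who has it without imputing anything. As planned, β0, the post-randomization effect β0 + β1 and the omnibus test forgo that adjustment. For β0 the loss is precision and chance-imbalance control; for the in-HCS part of the post-randomization contrast it is avoidable confounding by prior acute care. The documents quantify neither, and the figures above rest on assumed variance shares, an assumed 1.5-fold imbalance and an assumed exponent.

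The documents do not support extending this to the primary Objective 2 result, and SAP 5.5.3 calls these analyses exploratory. The change is worth making because the data are in hand and it moves the model back toward the protocol, not because a main conclusion depends on it.

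**What to change.** - In SAP 5.5.3, keep all patients and add (baseline value of the outcome) × I(in HCS before randomization) plus I(new to HCS), with baseline in the same form as in the 5.3 model. For Table 4 use baseline days of OUD treatment in the same way.
- Reword 5.5.2 to say that patients new to the HCS cannot be baseline-adjusted, and amend notes a and b of Tables 4 and 5.
- Keep the demographics-only model as a supplementary row and report 5.5.4.a beside it.

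If only b × (1 − period) is adopted, say that it repairs the pre-randomization effect and its part of the omnibus test and leaves the confounding untouched.

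The cost is SAP wording and two coefficients, with no new data. Patients new to the HCS remain without baseline adjustment, and their entry to the sample may depend on the intervention, so the post-randomization contrast stays observational and should still be labelled so.
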